3.4 Equipment Information (PET)

The ADVANCE (General Electric Medical Systems) whole body PET scanner consists of 336 BGO detector units arranged to form 18 rings (separated by 1 mm retractable tungsten septa) with 672 crystals each, giving 35 contiguous 2-D image planes through an axial field of view of 15.2 cm. The maximum transaxial FOV is 55 cm in diameter through a 58 cm diameter patient port. The average axial resolution (FWHM) is 4.2 mm at $r=0$ cm; 5.5 mm at $r = 10$ cm; and 6.6 mm at $r = 20$ cm. Total system sensitivity is 223 Kcps/uCi/cc with septa in and 1200 Kcps/uCi/cc with septa out. Reconstruction time is <2 seconds per 4.25 mm slice at 128x128 pixels.(22,23)

3.5 Standard Evaluation Schema

The initial evaluation of a patient with progressive disease be it locoregional or metastatic, androgen dependent or independent, is directed toward determining disease extent and pattern of spread. This usually consists of a history and physical examination, a hematology, chemical and PSA profile, and for patients with androgen independent disease, a serum testosterone level. Imaging studies typically include a chest radiograph, a CT of the abdomen and pelvis, and radionuclide bone scan. To assess the prostate and pelvic lymph nodes, magnetic resonance imaging is recommended, because CT scanning is too insensitive to accurately reflect the presence or absence of disease, and to determine local extent within the prostate itself. Our experience to date shows that frequently, magnetic resonance imaging of the pelvis is negative, and because some patients do not have pelvic disease, we will only advise this test when clinically indicated. Further, because the results of CT and/or MR imaging do not change in the two week interval following an intervention, we will no longer require that all studies be completed prior to the performance of the PET scan. The presence or absence of other medical co-morbidities, such as cardiac or pulmonary disease, frequently mandates additional testing in this patient population.

4.0 BACKGROUND DRUG INFORMATION

4.1 ¹¹C-methionine: L-methyl-¹¹C-methionine has undergone general safety testing. The preparation is apyrogenic and sterile, and is prepared in a form suitable for injection. It is formulated by the radiochemistry/cyclotron facility using established procedures. The individual patient doses will be tested by appropriate quality control procedures to ensure expected potency, purity, and apyrogenicity. An IND is not required at this time, as this study will be submitted for authorization and approval under the MSKCC Committee on radiation (Title 21, Part 361.1 of the Federal Code of Regulations). The product is produced at high specific activity, has been used on multiple occasions in humans at other centers, and has no evidence of pharmacological effect.

4.2 [¹⁸F]-fluoro-2-deoxy-D-glucose: FDG has undergone general safety testing, is approved by the FDA, and is on the hospital formulary for use as a diagnostic agent.

4.3 [¹⁸F]-dihydrotestosterone (FDHT): Dihydrotestosterone is the predominant testosterone that is present in the prostate gland itself in animals. Welch, Katzenellenbogen and their colleagues have developed a variety of tracers for study of the androgen receptor. Preclinical evaluation of a variety of fluorinated steroids was undertaken in baboons. 16 β -[¹⁸F]-fluoro-5 α dihydrotestosterone (FDHT) appeared to be the preferred agent in mammals due to favorable biodistribution and demonstrable androgen receptor binding. The plasma protein sex-hormone binding globulin (SHBG) is found in high concentration in primates in contradistinction to rodents. Plasma SHBG may therefore explain the higher uptake of FDHT into baboon prostatic tissue in comparison to other fluorinated steroids possibly related to reduced metabolic breakdown. The activity of FDHT in the region of the prostate peaked at 30-90 minutes post injection. At 60 minutes there was a high ratio of prostatic activity to soft tissue, blood and bone (>6:1, >3.5:1 and >7:1 respectively).(24,25) It appears that the ligand FDHT exhibits sufficient specific binding to androgen receptors *in vivo* to allow imaging of androgen receptor-positive tissue. Accordingly, in the orchiectomized host, where androgen receptor occupancy would be expected to be low, it seems feasible to image androgen receptor-positive human cancers. A protocol for the usage of this tracer in humans has yet to be developed. Using dynamic imaging with venous blood sampling we will determine the feasibility of use of this tracer in humans.

Washington University has initiated a clinical trial, and has studied 6 patients with PET imaging. The study is done under the auspices of the Washington University Radioactive Drug Research Committee ([name], Chairman), and this has been the basis for the dosimetry reported in the Appendices. No toxicity has been observed.

5.0 PATIENT ELIGIBILITY

5.1 Entry requirements:

5.1.1 Patients with histologically confirmed prostate adenocarcinoma.

5.1.2 Disease progression as demonstrated by:

5.1.2.1 A \geq 50% increase in PSA which is sustained for a minimum of 3 observations obtained at least 1 week apart;

OR

5.1.2.2 Development of new lesions or an increase in pre-existing lesions on bone scintigraphy, or in measurable disease by CT or MRI.

5.1.3 Karnofsky performance status > 60%.

5.1.4 Informed consent.

5.2 Exclusion Criteria:

5.2.1 Patients with an active infection not controlled by antibiotics.

5.2.2 Patients with clinically significant pulmonary or cardiac (NYHA Class III or IV) disease.

6.0 PRETREATMENT EVALUATION

6.1 History and physical examination

6.2 Laboratory studies: CBC, PSA (within 2 weeks of study entry); serum testosterone (within 4 weeks of study entry).

6.3 Urinalysis (if normal, no culture required) to exclude urinary tract infection (within 2 weeks).

6.4 Bone scintigraphy (within 6 weeks of study entry or up to 2 weeks after entry); using the MSKCC bone scan index (appendix D)

6.5 Computed tomography of abdomen and pelvis (within 6 weeks before entry or up to 2 weeks after entry) and/or Modified MRI of the pelvis to image the prostate (includes retroperitoneum) at MSKCC within 6 weeks before entry or up to 2 weeks after entry as clinically indicated.)

6.6 Chest radiograph (within 6 weeks before entry or up to 2 weeks after entry)

7.0 TREATMENT PLAN

7.1 Patients will be fasting for 6 hours prior to PET imaging, with the exception of liberal water intake which is encouraged.

7.2 A blood glucose level will be obtained prior to FDG administration. Elevated baseline serum glucose levels have been reported to cause false negative results with FDG-PET imaging.

7.3 An intravenous catheter (heplock) will be placed in the nuclear medicine department for radiopharmaceutical administration and blood sampling.

7.4 ¹¹C-methionine: Each patient will receive 10 -15 mCi of ¹¹C-methionine intravenously with PET imaging beginning 10 minutes after the injection, for approximately 60 minutes total using standard imaging procedures, as described (B).

FDG: Each patient will receive 10 mCi of FDG intravenously followed by PET imaging for a total imaging time of approximately 60 to 75 minutes using standard imaging procedures.

- 7.5 Patients will be imaged using the ADVANCE (General Electric Medical Systems) whole body PET scanner.
- 7.6 The radiopharmacy will keep a log of all doses administered.
- 7.7 The intravenous catheter will be removed at the conclusion of imaging.
- 7.8 Unless otherwise specified by a clinical trial, patients can undergo serial scans 4 weeks, 12 weeks, and 6 months following the baseline scan. If the patient is receiving treatment on a clinical trial, then PET scanning will be performed according to the schedule outlined in the treatment trial. No more than 7 repeat studies will be performed in a one-year period. This ensures that the total exposure is less than 15 rads to the organ receiving the highest radiation dose per year (the left ventricle) (See appendix).
- 7.9 Baseline ^{18}F -FDHT scans can be performed within two weeks of a baseline FDG scan, as long as there has been no change to the patient's treatment in the interim. Those patients selected for serial PET imaging with ^{18}F -FDHT will have all additional ^{18}F -FDHT scans performed the day after the FDG scan. An index lesion will be selected from the previous CMET or FDG scan. The patient will be positioned on the scanner, with the index lesion positioned at the center of the 14.25 cm field of view. A 5 minute transmission scan will be performed to verify the correct location of the patient on the scanner. A dynamic PET image acquisition will be initiated immediately post injection with 10 mCi (370 MBq) of ^{18}F -FDHT, to evaluate the rate of ^{18}F -FDHT uptake in the index lesion. Dynamic scans consisting of 10 one-minute, and 10 five-minute frames will be acquired (total duration = 60 minutes). Up to a maximum of 17 serial blood samples will be taken at the following collection times when possible: 0, 0.5, 1, 1.5, 2, 3, 4, 5, 7, 10, 15, 20, 30, 40, 50, 60, and 120 minutes post injection. Blood samples will be counted on a well scintillation counter (LKB Wallac), to determine the blood clearance kinetics of the radiotracer. After the dynamic scan, a whole body scan will be performed, either in immediate continuation or following a short rest, if required by the patient. The whole body scan will follow our department ^{18}F -FDG guidelines of 6-minute emission and 4-minute transmission scans per field-of-view. In selected patients, additional views, partial or total body, will be acquired between 2-4 hours post injection when possible, to assess retention of the tracer in the tumor. All images will be reconstructed by filtered backprojection and iterative reconstruction, with attenuation correction. The kinetics of tumor uptake will be determined by region-of-interest (ROI) analysis of the dynamic image data set. This data will provide plots of the tumor relative specific activity ($\mu\text{Ci}/\text{cc}$ of the ^{18}F -FDHT) versus time post administration. Region-of-interest analysis over tissues e.g. brain, heart, liver, spleen, kidney, bladder, muscle and tumor on the decay corrected whole body images will enable relative uptake ratios (tumor/normal tissues) of the ^{18}F -FDHT to be determined at between 1-2 hours post ^{18}F -FDHT injection. Changes in the absolute tumor uptake of ^{18}F -FDHT per unit administered dose relative to normal organs should reflect changes in androgen level expression in the tumor.
- 7.9.1 Patients will have a testosterone, sex hormone binding globulin, and DHT level drawn within 2 weeks prior to any FDHT scan.

**8.0 TOXICITY ASSESSMENT AND MANAGEMENT**

8.1 No toxicity is anticipated with the described radiopharmaceutical preparations or PET scanning. The formulations and doses of radiotracers are below defined levels for radiation toxicity. (Title 21,361.1).

8.2 Dosimetry Assessment: The total rad dose is below the limits set by the FDA for investigational radioactive drug studies, and falls within the Radioactive Drug Research Committee guidelines as defined by 5 rad/single organ/dose and 5 rad/year to the whole body, hematopoietic organs, gonads and eyes.

9.1 SERIOUS ADVERSE EVENTS (SAE) REPORTING

Any SAE must be reported to the IRB as soon as possible but no later than 5 calendar days. The IRB requires a Clinical Research Database (CRDB) AE report to be delivered to the Institutional SAE Manager ([name]) containing the following information:

Fields populated from the CRDB:

- Subject's name (generate the report with only initials if it will be sent outside of MSKCC)
- Medical record number
- Disease/histology (if applicable)
- Protocol number and title

Data needing to be entered:

- The date the adverse event occurred
- The adverse event
- Relationship of the adverse event to the treatment (drug, device, or intervention)
- If the AE was expected
- The severity of the AE
- The intervention
- Detailed text that includes the following information:
 - A explanation of how the AE was handled
 - A description of the subject's condition
 - Indication if the subject remains on the study
 - If an amendment will need to be made to the protocol and/or consent form

The PI's signature and the date it was signed are required on the completed report.

For IND/IDE protocols:

The CRDB AE report should be completed as above and the FDA assigned IND/IDE number written at the top of the report. The report will be forwarded to the FDA by the Institutional SAE Manager through the IND Office.

10.0 CRITERIA FOR REMOVAL FROM STUDY

Patients will be removed from the study at their request or for failure to comply with protocol requirements.

This analysis will be used on all selected PET scans, including retrospectively analyzing PET scans received prior to patient registration.

12.0 BIOSTATISTICAL CONSIDERATIONS

To assess the diagnostic implications of PET scanning with ¹¹C-methionine and FDG, the sensitivity and specificity will be estimated by comparing PET scan results to "standard of care" diagnostic measures that include the 99m-Tc bone scan, computed tomography, and magnetic resonance imaging. Each patient will receive these standard diagnostic measures and PET scanning with both ¹¹C-methionine and FDG. The diagnostic

"standard of care" scan (bone scan, CT or MRI) will be recorded as positive or negative for each site: bone and bone marrow and/or soft tissue

The sensitivity of PET imaging with ^{11}C -methionine or FDG is defined as the ability of PET scanning to identify those metastatic lesions diagnosed by standard diagnosis using bone scan, CT, or MRI as "gold standard" and is determined by the proportion of patients with positive lesions as diagnosed by standard method who were identified by the PET imaging. The sensitivity will be measured for both androgen-dependent and androgen-independent prostate cancer patients, and on a site by site basis (bone and bone marrow, and soft tissue).

Assuming at least one site in each patient is assessed positive by the gold standard, the sensitivity of FDG and ^{11}C -methionine can be conservatively estimated to within ± 0.16 . The total sample size for this study is 265.

To explore changes in metabolism during treatment based on PET imaging, the average SUV value will be recorded at 4 weeks, 12 weeks, and 6 months following the baseline scan. Summary measures such as the slope of the SUV trajectory and the area under the SUV curve will be recorded separately for FDG and ^{11}C -methionine.

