Initially, we will define the degree of correlation between FDG or C-11-methionine and standard imaging modalities such as CT/MRI and bone scans. We have observed discordance between uptake of [¹¹C]-methionine (CMET) and FDG in individual sites.(1) Pilot studies have given us a basis for estimates of variability and differences between FDG and CMET, and kinetic data has led to the design of acquisition protocols that make whole body PET imaging of CMET practical in patients. As such, we will continue to compare on a site by site basis the uptake of ¹¹C-methionine and FDG by performing whole body PET imaging following each radiopharmaceutical administration. Comparisons will be made to bone scintigraphy using 99m-Tc scanning, computed tomography, and, when clinically indicated, magnetic resonance imaging to assess whether sites detected by PET imaging are identified using standard imaging techniques and *vice versa*. Also, where tumor sites are identified on PET scans, a semiquantitative index, the standardized uptake value (SUV), as well as related parameters of total lesion metabolism (TLM) will be calculated as an objective measurement. In selected patients, imaging will be performed with F-18 fluoro dihydrotestosterone (FDHT), obtained through a collaboration with [name]. of Washington University, St. Louis.(2)

We will also define the utility of PET as an outcome measure following treatment by assessing the effects of treatment on SUV. Selected patients will be asked to undergo follow-up PET scanning along with follow-up bone scintigraphy, CT or MRI, where clinically appropriate.

All patients with histologically documented progressive prostate cancer are eligible, including those with localized disease, rising PSA, non-castrate metastatic, and castrate metastatic disease. Progression may be defined either by a rise in PSA of $\geq 50\%$, development of new bone lesions or an increase in pre-existing lesions, or an increase in measurable disease.

Patients will undergo PET scanning using either FDG either alone or with CMET or DHT (performed the day following the FDG scan). Serum will be drawn to define the pharmacokinetic properties of the tracer. Serial PET scans will be performed at baseline, four weeks, and twelve weeks and six months, in conjunction with bone scanning, CT/MRI, where clinically appropriate, unless the patient is on a clinical trial that dictates otherwise. These will be compared with baseline scans and available prior scans .

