One hypothesis under study in this trial is whether ¹¹C- methionine is more effective in visualizing androgen independent prostate cancer by PET imaging. The essential amino acid, ¹¹C- methionine is a tracer that has been used to image a variety of human tumors.(16-18) In a preliminary report from Nilsson and coworkers, 12 patients with androgen independent prostate cancer underwent PET imaging with ¹¹C- methionine. Uptake of the radiotracer was discovered in all known sites of bone and soft tissue lesions of patients visualized by standard bone scintigraphy or cross sectional imaging.(19) Ten patients had repeat PET scans. Those who responded to treatment had a reduced uptake of the radiotracer with no changes in the images generated by standard techniques. Our ongoing results show that 93% of index lesions were visible using ¹¹C-methionine and 83% visible using FDG.(1) These biodistribution and metabolic findings require additional verification in a larger series.

¹¹C-methionine and ¹⁸FDG whole body imaging

We have performed a preliminary comparative study of ¹¹C-methionine and ¹⁸F-FDG in 10 patients with prostate cancer, who were referred for PET imaging with progressive prostate cancer, as defined by serially rising PSA values and one or more new ("index") lesions on bone scan. Among the 10 patients, there were 13 such index lesions on bone scans. ¹¹C-methionine imaged 12/13 (93%), and ¹⁸F-FDG 11/13 (83%) index lesions. The one lesion not imaged by CMET was subsequently judged to be avascular necrosis, based on its pattern of resolution on subsequent bone scans. ¹¹C-methionine is very rapidly cleared from the blood, with rapid equilibration (10 minutes) in the tumor. The tumor uptake of ¹¹C-methionine is consistently high, with standard uptake values (SUVs) ranging from 4.9 to 11.6. We have therefore shown that high-quality whole body PET imaging is feasible with ¹¹C-methionine, despite the short 20-min physical half-life of carbon-11.

As accrual to the study has been limited by the need to generate ¹¹C-methionine immediately prior to administration, and based on our preliminary results showing that a higher percentage of tumors are visualized with FDG than previously anticipated, we plan to perform FDG scans in all patients, and ¹¹C-methionine when it is available. In cases where uptake is visible with FDG, repeat studies will be conducted after therapeutic intervention.

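### Section 12.0 assumes both tracers in every patient and gives one ±0.16 for both, but the methionine number is unstated and ±0.16 does not correspond to FDG in 265 patients

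*Combined protocol and SAP*

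**What the plan says.** Section 12.0 describes a fully paired design: "Each patient will receive these standard diagnostic measures and PET scanning with both" methionine and FDG. Sensitivity is defined as a proportion of patients: those positive on bone scan, CT or MRI whom PET also identifies. Assuming that every patient has at least one such positive site, the section says the sensitivity of the two tracers "can be conservatively estimated to within" ±0.16. The next sentence reads "The total sample size for this study is 265". No confidence level, assumed sensitivity or sample size is attached to the ±0.16.

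Other parts of the document describe a different allocation:

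- Section 1.0, Protocol Summary: "Patients will undergo PET scanning using either FDG either alone or with CMET or DHT".
- Section 2.0, the objective on diagnostic ability: FDG is assessed generally, methionine only in selected cases.
- Section 3.3, under whole body imaging: "we plan to perform FDG scans in all patients, and" methionine when it is available. A reason is given, beginning "As accrual to the study has been limited by the need to generate" the tracer just before use.

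Section 7.4 introduces both tracers as something each patient receives. This may only describe the procedure for those who are scanned, but it can also be read as agreeing with Section 12.0.

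Objective 2.2 sets out to determine which of the two tracers better predicts treatment response.

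**The concern.** A precision statement depends on its denominator. If methionine goes to a subset, the two tracers have different denominators, and one half-width cannot describe both unless it is only an upper bound. The document never says how many patients will have methionine, so a reader cannot judge how well its sensitivity will be estimated. For FDG the sample size appears to be known, yet the stated half-width looks far too wide for it.

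The comparison in objective 2.2 is also affected. Only patients scanned with both tracers carry within-patient information on FDG versus methionine. Section 12.0 records the SUV summaries separately by tracer and names no analysis set for a contrast. If FDG results from all patients were set beside methionine results from a subset, a difference in case mix could be read as a difference between tracers.

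**Working it through.** **Inputs.** From Section 12.0: half-width 0.16 for both tracers; total N = 265; patient as the unit; every patient assumed positive on standard imaging. Assumed, because not stated: sensitivity p = 0.5 (the worst case, which the word for conservative estimation suggests) and two-sided 95% confidence, with 90% and 99% alongside.

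**Step 1: try to reproduce ±0.16 from 265.** Half-width = z × √(p(1−p)/n), with √(0.25/265) = 0.0307.

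- 90%: 1.645 × 0.0307 = 0.051
- 95%: 1.960 × 0.0307 = 0.060
- 99%: 2.576 × 0.0307 = 0.079

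The plan's figure is not reproduced. At 95%, a Wilson interval gives ±0.060 and an exact (Clopper-Pearson) interval ±0.062. A Bonferroni adjustment over eight estimates gives ±0.084. A sensitivity away from 0.5 only narrows the interval: p = 0.83 gives ±0.045 at 95%.

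**Step 2: find the n that ±0.16 implies.** n = 0.25 × (z/0.16)².

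- 90%: 26.4, so 27
- 95%: 37.5, so 38
- 99%: 64.8, so 65

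At 95%, 38/265 = 14% of the stated total. Wilson, exact and continuity-corrected intervals move the 95% figure to between about 32 and 46. If the sensitivity were 0.83 instead of 0.5, 22 patients would be enough at 95%.

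**Step 3: methionine.** Its n is unknown, so only a range can be shown (p = 0.5, 95%, n assumed):

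| Standard-imaging-positive patients scanned with methionine | Half-width |
|---|---|
| 20 | ±0.219 |
| 30 | ±0.179 |
| 38 | ±0.159 |
| 50 | ±0.139 |
| 100 | ±0.098 |
| 150 | ±0.080 |
| 265 | ±0.060 |

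The stated ±0.16 is met from about 38 upwards and missed below that.

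**Step 4: FDG.** Section 3.3 gives FDG to all, so the methionine subset does not change its n. What can change it is the number positive on standard imaging. The Protocol Summary admits patients with localized disease or rising PSA, and some of them may have no positive site. With 200 positive patients the half-width is ±0.069, with 150 it is ±0.080, and with 100 it is ±0.098 (these counts are assumed). At 95% the denominator would have to fall to about 38 before ±0.16 described it.

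**Step 5: the tracer contrast.** Under Section 3.3 every methionine patient also has FDG, so the comparison is fully paired inside the methionine subset and unpaired nowhere else. The cohort outside that subset adds FDG information only.

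**The case against.** The strongest reply is that ±0.16 and 265 stand in separate sentences and need not belong together. The preceding text breaks sensitivity down by patient group: "The sensitivity will be measured for both androgen-dependent and androgen-independent prostate cancer patients", and also by type of site. The ±0.16 might describe a subgroup or a target of about 38 patients. This cannot be excluded. An even split of 265 by androgen status gives ±0.085, four even parts give ±0.120, and about seven are needed to reach ±0.16. Section 12.0 describes no such split, although uneven groups could be smaller. What stands is that the n behind ±0.16 is unstated. The reply does not supply one.

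A second reply is that the plan calls the estimate conservative, so for FDG the figure is a safe bound. That is correct. A reader might infer that the methionine subset spoils the precision for both tracers, or that ±0.16 overstates how well FDG will be estimated. The document supports neither reading: FDG goes to everyone under Section 3.3, and ±0.16 is wider than what 265 patients deliver. The FDG figure is uninformative, not optimistic.

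A third reply is that the tracer comparison is already within patient, because the Protocol Summary plans it site by site with a whole body scan after each tracer. This also has force. A reader might infer that a biased comparison of all-patient FDG with subset methionine is planned. It is not, and the size of any such bias cannot be worked out from the document. What is missing is an explicit restriction to patients scanned with both. Most aims are worded as exploratory, but objective 2.2 is worded as a determination.

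**Conclusion.** The contradiction is in the current text, and nothing elsewhere resolves it: Section 12.0 requires both tracers in each patient, while Sections 1.0, 2.0 and 3.3 do not. The two consequences should be kept apart.

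- **Methionine:** ±0.16 is conditional on about 38 or more standard-imaging-positive patients at 95% (27 at 90%, 65 at 99%; p = 0.5 assumed). The plan commits to no number, so the precision is unknown. It has not been shown to be inadequate.
- **FDG:** ±0.16 does not correspond to 265, which gives about ±0.060 at 95% (±0.051 at 90%, ±0.079 at 99%). That is the best case, because it needs all 265 to be positive on standard imaging.

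This should be fixed. It does not invalidate the study, but a stated design rule and a stated precision cannot be used as written, and a comparative objective has no defined analysis set. Confidence in the contradiction and the arithmetic is high. The confidence level and p remain assumptions.

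**What to change.** 1. Reconcile Section 12.0 with Sections 1.0, 2.0, 3.3 and 7.4 on who receives methionine, and state the expected number of patients scanned with both tracers.
2. Replace the single ±0.16 with a separate half-width for each tracer. Base each on the expected number of standard-imaging-positive patients scanned with that tracer, and name the confidence level and the assumed sensitivity.
3. Restrict every FDG versus methionine contrast, including the one in objective 2.2, to patients scanned with both. Use a paired analysis that allows for several lesions within a patient; GEE is one option. Report the all-patient FDG results separately.

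The cost is wording, with no added scans. The downside is that fewer patients inform the tracer comparison, so its interval will be wider, and the claim in objective 2.2 may need softer wording.

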3.2 Conventional Imaging Modalities

Radionuclide bone scanning: Standard bone scintigraphy is limited because it reflects the reaction of bone to surrounding cancer rather than providing a direct measure of cancer activity. In one series of patients with a total of 100 bone scan abnormalities, 57 were confirmed by plain radiographs, and 42 showed normal corresponding plain radiographs; and 1 patient had a radiographic abnormality not detected by scintigraphy.(10) The flare phenomenon, a paradoxical increase in intensity after successful therapy, further complicates the interpretation of scans on a serial basis.(11) To begin to address these questions, we have developed a novel bone scan index,(12) which quantifies the percentage of bone involved by tumor, but this too does not provide an index of the viability of tumor.

Cross sectional imaging: Cross-sectional imaging modalities used in the evaluation of prostate cancer include computed tomography (CT) and magnetic resonance imaging (MRI). The utility of each of these modalities varies according to stage of the disease. CT is well suited for the detection of soft tissue disease, but has limited utility in assessing early changes in bone. It is not sensitive in detecting microscopic nodal disease or for detecting tumor in non-enlarged lymph nodes. In our experience, CT is also limited in evaluating disease confined to the prostate and adjacent area. MRI imaging is considered the modality of choice for the most accurate assessment in the region of the prostate, neurovascular bundles and seminal vesicles.(13) MRI can also detect soft tissue disease and is most useful to corroborate bone scintigraphic findings, since the earliest involvement is thought to be present in the bone marrow. MRI exhibits the highest sensitivity in the axial skeleton and pelvis, and is less effective in the ribs, chest wall, and skull.

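### Section 12.0 says every patient has bone scan, CT and MRI, but MRI is done on clinical indication, so the pooled reference standard differs between patients

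*Combined protocol and SAP*

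**What the plan says.** Section 12.0 plans to estimate the sensitivity and specificity of PET against standard measures "that include the 99m-Tc bone scan, computed tomography, and magnetic resonance imaging". It then states: "Each patient will receive these standard diagnostic measures and PET scanning with both" methionine and FDG. The standard scan is recorded as positive or negative for each site class (bone/marrow, soft tissue), and a positive result on any of the three tests serves as the reference for sensitivity.

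Three other current sections describe MRI differently:

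- Section 1.0 lists the comparators as bone scan, "computed tomography, and, when clinically indicated, magnetic resonance imaging".
- Section 3.5 says that pelvic MRI has often been negative, and continues: "because some patients do not have pelvic disease, we will only advise this test when clinically indicated".
- Section 6.5 lists CT of abdomen and pelvis "and/or Modified MRI of the pelvis to image the prostate", the MRI again subject to clinical indication.

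Bone scintigraphy is listed in Section 6.4 without any such condition.

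**The concern.** Diagnostic ability against standard imaging is one of the primary objectives in Section 2.0. An accuracy estimate means the same thing in all patients only if the reference means the same thing in all patients. Here the reference is a composite whose content varies, and the test that varies is the one the protocol regards as the better one for the prostate region. Whether a patient gets it depends on suspicion of the very disease being verified.

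Two errors can follow. In a patient without MRI, a true PET finding that CT missed is scored as a false positive. In a patient with MRI, disease that only MRI shows enters the sensitivity denominator, where PET may do better or worse than on disease that CT or bone scan also shows. The pooled figures then partly reflect how often, and in whom, MRI was ordered.

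**Working it through.** The plan gives no MRI rate and no MRI yield, so it has no figure on this point to reproduce. The check is a comparison of sections, followed by an illustration with assumed inputs.

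**1. Is MRI universal?** Section 12.0: yes, for each patient. Sections 1.0, 3.5 and 6.5: no, on clinical indication. These cannot all hold. The wording of Section 6.5 can also be read as leaving CT non-universal.

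**2. Is MRI use related to disease?** Yes. Section 3.5 gives as a reason for conditional MRI that some patients have no pelvic disease.

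**3. Does MRI change the reference?** In an any-positive composite, adding a test can only add positives. Section 3.5 regards CT as not sensitive enough for the prostate and pelvic nodes. Section 3.2 prefers MRI in the prostate region and places the earliest bone involvement in marrow. Section 11.0 records nodes, soft tissue masses and bone metastases from MRI. A patient without MRI normally still has bone scan and CT, so these regions are verified less sensitively, not left unexamined.

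**4. On what unit?** Section 12.0 defines sensitivity as a proportion of patients, by site class, although it also speaks of lesions and of a site-by-site analysis. On the patient reading, MRI matters only where it alone turns a site class positive.

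**5. Illustration for one site class, such as soft tissue.** All inputs are assumptions:

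- q = share of truly positive patients found by bone scan or CT: 0.6 to 0.8
- s1 = PET sensitivity in those patients: 0.83
- s2 = PET sensitivity in patients positive on MRI only: 0.50, then 0.83 and 0.93
- π = prevalence: 0.3 to 0.5
- true PET specificity: 0.90
- MRI, where done, finds all the remaining disease

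Apparent sensitivity is s1 without MRI and q·s1 + (1 − q)·s2 with MRI.

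| s2 | Without MRI | With MRI, q = 0.6 | With MRI, q = 0.8 |
|---|---|---|---|
| 0.50 | 0.83 | 0.498 + 0.200 = 0.698 | 0.664 + 0.100 = 0.764 |
| 0.83 | 0.83 | 0.83 | 0.83 |
| 0.93 | 0.83 | 0.498 + 0.372 = 0.870 | 0.664 + 0.186 = 0.850 |

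Apparent specificity without MRI is [(1 − π)·0.90 + π(1 − q)(1 − s2)] / [(1 − π) + π(1 − q)]. With s2 = 0.50:

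- q = 0.6, π = 0.5: (0.45 + 0.10) / 0.70 = 0.786
- q = 0.8, π = 0.3: (0.63 + 0.03) / 0.76 = 0.868

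With MRI it is 0.90 by construction. PET performance is the same in both groups in every case; only the reference differs. For sensitivity, even the sign of the difference turns on s2, which the documents do not give.

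**6. Does the plan handle it?** Sections 11.0 and 12.0 contain no rule for a patient without MRI: no common reference set, no reporting by tests performed, and no category for a site that was not covered.

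**The case against.** The reference is worded as bone scan, CT or MRI, so it can be formed without MRI. Section 11.0 has each modality read and recorded independently, and Section 12.0 splits sensitivity by site class, so modality-matched results could be produced from the planned data. The objectives are exploratory. All of this is fair and limits the consequence. It does not make the Section 12.0 sentence true, and data that could support a matched analysis are not a plan to do one.

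A reader might infer four stronger things that the documents do not support.

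- *That nothing examines the pelvis or marrow without MRI.* Bone scan is unconditional and CT normally covers the pelvis. Section 3.2 says "MRI can also detect soft tissue disease and is most useful to corroborate bone scintigraphic findings", so many MRI bone lesions would already be positive on bone scan.
- *That PET sensitivity must be lower in MRI patients, by an amount obtainable from the 71% FDG concordance in Section 3.4.* That figure counts bone-scan lesions (157 lesions in 18 patients). Adding pelvic MRI lesions to it mixes site classes and does not match a patient-level definition. Section 3.5 also reports that pelvic MRI is often negative, which suggests a modest yield, and MRI lesions must be bidimensionally measurable to be recorded.
- *That comparisons across disease states are shown to be confounded.* Section 12.0 reports sensitivity for androgen-dependent and androgen-independent patients but plans no formal test, and MRI use by disease state is not given. Confounding is possible, not shown.
- *That CT alone should be the soft-tissue reference.* Used by itself, it would score as false positive a pelvic PET finding that MRI confirmed and CT missed.

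**Conclusion.** Wrong as written. Section 12.0 contradicts Sections 1.0, 3.5 and 6.5 on whether every patient has MRI, and the contradiction bears on a primary objective. That the reference varies with MRI use follows from the text. That it is more sensitive with MRI rests on the any-positive reading of the reference and on the protocol's own account of CT and MRI. The effect is concentrated in pelvic and retroperitoneal soft tissue, with a smaller part in pelvic bone and marrow.

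The size is open. In the illustration, apparent sensitivity with MRI differs from that without it by between −0.13 (0.698 − 0.83) and +0.04 (0.870 − 0.83), and apparent specificity without MRI falls short of 0.90 by 0.03 to 0.11. These figures show that the effect can matter; they are not estimates for this trial. Confidence is high for the contradiction and the missing rule, and low for any particular bias.

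**What to change.** In Section 12.0:

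1. Replace the sentence with one stating that MRI is done when clinically indicated, in line with Sections 1.0, 3.5 and 6.5. State whether CT is expected in every patient, since Section 6.5 is ambiguous on this. The same sentence promises both tracers to everyone, whereas Section 3.3 plans methionine only when available; those passages must be reconciled too.
2. For each patient and site class, record which reference tests were done and, for MRI, why.
3. Report sensitivity and specificity by site class on a common bone-scan-plus-CT reference, in patients who had both tests.
4. Report separately, in the MRI subset, PET against the reference with MRI included.
5. Classify a site that no performed test covered as not evaluable, not as negative.

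This needs no added scans and no change to patient care, only wording and a field on the data form. The cost is smaller denominators for the MRI-based estimates. Two limits should be stated with the results. The MRI subset is selected by clinical suspicion, so its figures describe that subset only. The common reference still misses disease that CT cannot show, which is why both analyses should appear side by side. Together they expose the dependence on MRI use but do not correct for it.
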